10.2 Time required to perform sinonasal cavity debridement for ethmoid cavity

During postoperative debridements in week 1, the research staff will record the time in minutes for each ethmoid cavity based on a video recording of the debridement. The debridement timing will start when the surgeon places the endoscope with a debriding instrument (suction or forceps) into the nasal cavity and ends when the surgeon stops removing any further packing, secretions, crusting, or blood from that ethmoid cavity. Two times will be recorded for each patient, one for each ethmoid cavity.

10.3 Bleeding During Debridement

The patient will be evaluated during the postoperative week 1 for bleeding during debridement via a recorded nasal endoscopy that will be evaluated by a blinded reviewer. Bleeding will also be assessed at week 4 if a second debridement is performed. The reviewer will grade bleeding during after debridement with the following scale:

Criteria	0	1	2	3
Bleeding	No bleeding	Minimal (confined to the nasal cavity)	Moderate (out of nasal cavity)	Severe (needs repacking or cauterization)

10.4 Postoperative healing assessment of mucosal edema, crusting, secretions, adhesions, and polyps

Nasal endoscopies will be recorded of each participant's ethmoid cavity at 1 week, 4 weeks, and 12 weeks and will be reviewed by a blinded reviewer to evaluate the healing of the ethmoid cavity. The reviewer will assess mucosal edema, crusting, secretions, and polyps using the validated Lund-Kennedy Endoscopy score. Adhesions will be evaluated as either present or absent in the middle meatus.

Criteria	0	1	2
Polyps in middle meatus	Absent	Restricted to middle meatus	Beyond the middle meatus
Discharge in middle meatus	Absent	Thin and clear discharge	Thick and purulent
Edema of the middle meatus	Absent	Mild-moderate	Moderate-severe
Crusting in middle meatus	Absent	Mild-moderate	Moderate-severe

Lund-Kennedy Endoscopy score

Criteria	0	1
Adhesions	No adhesion	Present in middle meatus

Adhesions Criteria

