Postoperative care of patients undergoing ESS is important both to minimize discomfort for the patients and to optimize long-term outcomes. Postoperative sinonasal cavity debridement has been advocated to prevent potential synechiae and sinus ostial stenosis, as well as to improve patient symptoms.³ Removal of old blood, nasal secretions, crusting, and unabsorbed packing are thought to reduce the inflammatory load, remove potential for scarring, and allow for improved access of topical medications. However, extensive debridement can cause bleeding, pain, and discomfort which may interfere with the effective execution of postoperative care. Furthermore, debridement is time consuming and may cause mucosal damage and thus delay the postoperative healing process.

Formation of adhesions, scarring, synechiae, middle turbinate lateralization, ostial stenosis and edema are major concerns often addressed by the use of bioresorbable packing postoperatively. Bioresorbable packing has been demonstrated to decrease the incidence of adhesions and bleeding while improving patient comfort compared to no packing at all.⁴ Commonly used bioresorbable packing placed in the middle meatus include chitosan-based nasal dressings such as PosiSep X. Bioresorbable nasal dressings have favorable wound healing characteristics and slowly degrade over time. However, bioresorbable nasal dressings oftentimes have not dissolved by the time of the first postoperative debridement 1-2 weeks after the surgery and therefore need to be manually removed. The removal of bioresorbable packing during postoperative debridements has similar levels of discomfort as the removal of traditional nonresorbable packing.⁵ While bioresorbable packing has advantages in preventing postoperative complications such as adhesions and bleeding, the packing is noticeably uncomfortable to remove for patients during postoperative debridements. An ideal nasal dressing would optimize both patient comfort as well as wound healing.

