3.0 STUDY DESIGN

3.1 Type of Study

This is a prospective randomized controlled multicenter study at the University of Southern California that will enroll at least 30 participants who satisfy criteria to compare the efficacy of PuraSinus versus standard of care in patients undergoing endoscopic sinus surgery. The study will utilize an intra-patient control design to assess the safety and efficacy of PuraSinus compared to PosiSep X on the contralateral side. The study patients will undergo PuraSinus placement in one nasal cavity following traditional endoscopic sinus surgery. The study is blinded, meaning that patients will be blinded throughout the study duration to which side received PuraSinus placement. The independent surgeon performing review of the video-endoscopies will also be blinded to which side received PuraSinus.

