10.1 Patient-reported pain during debridement

During postoperative debridements in week 1, the surgeon will topically anesthetize both nasal cavities. The surgeon will then begin debridement of the left ethmoid cavity, removing any residual packing, blood, secretions, obstructive crusting from that ethmoid cavity. The surgeon will then perform the same debridement in the right ethmoid cavity. Afterwards, the patient will be asked to rate their pain on a scale from 1-10 with 1 being the least pain and 10 being the most extreme pain during the procedure for each ethmoid cavity (left and right), which will be recorded by the research staff.

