10.5 Amount of residual PuraSinus or bioresorbable dressing in ethmoid cavity

At 1 week after surgery, the amount of residual PuraSinus or PosiSep X in the ethmoid cavity will be measured as none, less than 50% of ethmoid cavity, or 50% or greater of ethmoid cavity.

10.6 The need for further intervention postoperatively at week 4

At 4 weeks after surgery, a recorded nasal endoscopy will be performed of each participant's ethmoid cavity and reviewed by an independent, blinded rhinologist to evaluate whether the participant required a postoperative intervention.

A post-operative intervention is a composite endpoint that includes:

- Surgical intervention required to debride obstructive adhesions or scar tissue formation
- Oral steroid intervention is warranted to resolve recurrent inflammation or polypoid edema

11.0 SPECIAL INSTRUCTIONS:

Participant remuneration: Participants in the clinical trial will receive remuneration in the form of \$90 in gift cards. Participants will receive a \$30 VISA gift card after each postoperative visit (week 1, week 4, and week 12) for a total of \$90. The remuneration is to compensate the patient for parking fees and time associated with participating in all aspects of this trial.

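### The week 1 grade of bleeding during debridement is called blinded, but it requires footage of the removal step, where undissolved PosiSep X may reveal the side; the blinding cannot be relied on for this secondary endpoint.

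*Combined protocol and SAP*

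**What the plan says.** Section 10.3 assesses patients at week 1 "for bleeding during debridement via a recorded nasal endoscopy that will be evaluated by a blinded reviewer". It then says: "The reviewer will grade bleeding during after debridement with the following scale", followed by a 0 to 3 scale. The synopsis endpoint and section 13.2 also refer to bleeding during the debridement. Section 3.1 makes the general claim: "The independent surgeon performing review of the video-endoscopies will also be blinded to which side received PuraSinus".

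Other sections describe what the footage contains:

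- **10.1:** debridement of each cavity consists of "removing any residual packing, blood, secretions, obstructive crusting from that ethmoid cavity".
- **10.2:** the time for each cavity is read "based on a video recording of the debridement", so the removal is filmed. Timing "ends when the surgeon stops removing any further packing, secretions, crusting, or blood from that ethmoid cavity".
- **1.0:** the text says of bioresorbable dressings that they frequently "have not dissolved by the time of the first postoperative debridement 1-2 weeks after the surgery and therefore need to be manually removed". The synopsis gives PosiSep X as its example. Section 1.0 describes PuraSinus as a transparent hydrogel of which a thin layer is enough.
- **10.5:** at week 1, "the amount of residual PuraSinus or PosiSep X in the ethmoid cavity will be measured". Table 1 places residual packing in the row reviewed by the independent blinded surgeon and lists bleeding in a separate row.
- **12.1:** video files are coded by research ID and laterality. No other handling is described.

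**The concern.** A grade of bleeding during removal cannot be made without seeing the removal. If one cavity visibly yields packing and the other does not, the picture itself suggests the allocation. Because each patient receives one product per side, identifying one cavity identifies the other. Neutral file names do not help when the cue is in the footage.

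Bleeding is one of the complications named in the secondary objective, and section 1.0 hypothesises that its incidence is the same with both products. A reader who can infer the product might grade one side more harshly, or might overlook a real difference. Either result would be reported as a blinded assessment. The phrase about grading during and after debridement also leaves open which part of the recording is scored.

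**Working it through.** The plan gives no figure for this point. Its power statement in 13.1 concerns pain and does not bear on it. The check is therefore mainly a comparison of sections.

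1. **Which footage is graded?** The heading and first sentence of 10.3, the synopsis endpoint and 13.2 all say during debridement. One sentence of 10.3 runs during and after together. On the plain reading, the removal is included.
2. **What does that footage show?** By 10.1 it shows residual packing being taken out. By the synopsis and 1.0, dressings such as PosiSep X are often still present and removed manually at the first debridement.
3. **Does the other side look the same?** Section 1.0 describes PuraSinus as thin and transparent, and expects it to need less debridement. A visible difference between the sides is part of the trial's rationale.
4. **Is there a safeguard?** Section 3.1 asserts blinding and 12.1 codes the files. Neither describes editing the clips, an order of grading or a check of blinding.
5. **How many patients?** The documents give no rate. As an assumption only, let q be the share of patients with visible undissolved packing. The number whose allocation could be inferred is 30 × q:

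| q (assumed) | Patients of 30 |
|---|---|
| 0.25 | 7.5 |
| 0.50 | 15 |
| 0.75 | 22.5 |
| 0.90 | 27 |

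6. **What would one altered grade do?** Section 13.2 presents bleeding as proportions. One patient moved from grade 0 to grade 1 on one side changes that side's proportion with any bleeding by 1/30 = 3.3 percentage points. Six such changes, all in the same direction, would move it by 6/30 = 20 points. This gives a scale only; nothing in the documents says how many grades would move, or in which direction.

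**The case against.** Several counter-arguments have force.

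**Unblinding is not certain.** The appearance of PosiSep X at week 1 is not described. Section 4.0 describes the clarity of PuraSinus as applied, not after a week among blood and crusts. Section 8.1.2 says PuraSinus will be removed at 1 week, and 10.5 allows for residue filling half the cavity or more. Material may therefore come out of both sides. This stands: the reader can probably infer the side where packing is visible, but not in every patient.

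**The grader may be someone else.** Table 1 lists bleeding outside the blinded surgeon's row, so the person grading residual packing need not be the person grading bleeding. This also stands, and it is an inconsistency to resolve. It does not rescue the claim, because 10.3 itself calls the bleeding reviewer blinded.

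**The scale is partly objective.** Bleeding out of the nasal cavity, or needing repacking or cautery, is largely observable. Judgement remains mainly between none and minimal, and over what counts as needing treatment.

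**A false-positive result does not follow.** A reader might infer that bias would produce a significant difference: six grades shifted one way give an exact two-sided sign test p of 2 × 0.5^6 = 0.031, and five give 0.063. The documents do not support that reading. Section 13.2 plans proportions for bleeding and names no test for it, although its general sentence on testing outcomes at 0.05 leaves some ambiguity. Purely one-way bias is an invention, since the stated hypothesis is equal bleeding.

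**Grading only after removal would replace the endpoint.** A reader might conclude that during should simply become after. By 10.2 the stop point comes when blood, too, is no longer being removed. Bleeding provoked by pulling packing could then be missed, perhaps mainly on the PosiSep X side. This stands, and the during-debridement grade should be kept.

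**Conclusion.** The week 1 grade of bleeding during debridement is described as blinded, but the plan does not reliably deliver that. The conclusion rests on the plain reading that the removal footage is graded, on the protocol's own account that the comparator often persists to that visit, and on the absence of any described masking. It assumes that undissolved packing can be distinguished on video from residual PuraSinus; this is likely but not documented.

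The share of patients affected and the size and direction of any bias are unknown. The effect is confined to how one secondary endpoint, reported as proportions, is described and interpreted. A reader might extend the point to the primary result, but pain is reported by the patient and is not scored from video. Other week 1 video ratings could share the exposure if packing is in view; the documents do not say which footage they use. The wording should be corrected, but the trial's main comparison is not in question.

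**What to change.** - Keep the synopsis endpoint of bleeding severity during the week 1 debridement. State in 10.3 that this grade is not reliably blinded, and report it that way.
- Replace the sentence that runs during and after together with two defined grades: one during debridement, and a separate one after debridement. Read the second from a clip of each cavity that starts once removal has ended.
- Fix the reading order. The reviewer scores the after-debridement clip first, before seeing any pre-debridement or removal footage, then the during-debridement grade, and residual dressing (10.5) last.
- Have staff note the stop timestamp when they read the 10.2 time, since 10.2 currently asks only for a duration in minutes. Keep the recording running briefly after removal ends, because no section now requires this.
- Reconcile Table 1 with 10.3 on who grades bleeding.

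The cost is minor clip trimming, slightly longer recording and one additional grade by the same reader. The masked grade will not capture bleeding that stops before removal ends, which is why it supplements the named endpoint and does not replace it.

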10.5 Amount of residual PuraSinus or bioresorbable dressing in ethmoid cavity

At 1 week after surgery, the amount of residual PuraSinus or PosiSep X in the ethmoid cavity will be measured as none, less than 50% of ethmoid cavity, or 50% or greater of ethmoid cavity.

10.6 The need for further intervention postoperatively at week 4

At 4 weeks after surgery, a recorded nasal endoscopy will be performed of each participant's ethmoid cavity and reviewed by an independent, blinded rhinologist to evaluate whether the participant required a postoperative intervention.

A post-operative intervention is a composite endpoint that includes:

- Surgical intervention required to debride obstructive adhesions or scar tissue formation
- Oral steroid intervention is warranted to resolve recurrent inflammation or polypoid edema

11.0 SPECIAL INSTRUCTIONS:

Participant remuneration: Participants in the clinical trial will receive remuneration in the form of \$90 in gift cards. Participants will receive a \$30 VISA gift card after each postoperative visit (week 1, week 4, and week 12) for a total of \$90. The remuneration is to compensate the patient for parking fees and time associated with participating in all aspects of this trial.

12.0 DATA COLLECTION AND MONITORING

12.1 Data collection forms

Data will be recorded onto a dedicated data collection form following the initial surgical procedure where PuraSinus and bioresorbable packing were used. The data on these anonymized forms will then be entered onto a secure password protected electronic database (REDCap) with appropriate back up systems and security protocols in place. No patient identifiable data will be stored on the database.

Endoscopic video data will be coded by the patient's research ID and laterality (right vs. left). No patient identifiable data will be used to label the video files, which will be stored on a secure university online database (Microsoft OneDrive).

12.2 Data management

Data collection forms will be transcribed into a dedicated encrypted electronic database and stored until 3 years after the study is completed with participant study charts. All electronic data will be stored on a password protected electronic database on computers with appropriate back up systems, anti-virus software and security protocols in place. The database will be backed up to an appropriate secure platform and no patient identifiable data will be stored on the database. Access to the database is restricted to participating investigators or a designated member of their research team.

13.0 STATISTICAL CONSIDERATIONS

13.1 Sample size

There are no published data available regarding trial outcomes for the PuraSinus hydrogel product. A study from Canada, reported pain during removal of a comparable bioresorbable packing (Nasopore) as 4.03/10 (SD 2.80) among 30 subjects.⁵ In our clinical practice, PosiSep X bioresorbable packing removal is usually rated approximately 5-6/10 (it is uncomfortable) and PuraSinus removal around a 2/10. Using a mean difference of 2 (4.03 with bioresorbable packing versus 2 with hydrogel), a more conservative SD of 3.5 and testing at a 2-sided alpha=0.05, a sample of 30 subjects will provide 83% power to detect this difference in paired measures using a Wilcoxon signed rank test.

13.2 Statistical analysis

The sample will be described by demographic and clinical characteristics, summarizing continuous variables by mean (SD) and categorical variable by frequency (percent). All trial outcome comparisons will be tested at a two-sided p-value of 0.05.

Primary objective: To investigate the efficacy of PuraSinus in reducing patient pain during postoperative debridement after endoscopic sinus surgery compared to PosiSep X.

The primary outcome of pain at 1-week debridement, evaluated on a 1-10 scale, will be compared between interventions using a Wilcoxon signed rank test (paired test). The median and interquartile range of the pain score will be summarized for each intervention. To consider side (right/left), a generalized linear mixed effects model will analyze the pain score as a dependent variable, with a random intercept for participant; independent variables will include randomized intervention, side, and an interaction of intervention-by-side (testing if the intervention effect may differ by side).

Secondary objectives:

- To assess the time needed to perform postoperative debridements in patients with PuraSinus in their ethmoid cavity after endoscopic sinus surgery
- To assess the efficacy of PuraSinus in preventing postoperative complications from endoscopic sinus surgery (adhesions, bleeding, crusting, edema)
- To assess the amount of PuraSinus retained in the ethmoid cavity postoperatively
- To assess the need for further intervention postoperatively in patients

Continuously measured secondary trial outcomes (time required for debridement; Lund-Kennedy Endoscopy score) will be compared between interventions using Wilcoxon signed rank and generalize mixed effects model as described above. Amount of bioresorbable dressing retained will be presented as proportions, with 95% confidence intervals (in the categories of none, <50%, ≥50%). Bleeding during debridement and adhesions will be presented as proportions. The need for further intervention will also be presented as proportion (with 95% confidence interval) of participants required further surgical or oral steroid intervention.

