6.0 STRATIFICATION/DESCRIPTIVE FACTORS/RANDOMIZATION SCHEME

6.1 The patient will undergo a bilateral operation. At the end of the surgery, hemostasis will be performed with PosiSep X placed in the ethmoid cavity on one side and PuraSinus in the other ethmoid cavity. The randomization will occur using the envelope method to determine which ethmoid cavity will receive PuraSinus and which ethmoid cavity will receive PosiSep X.

Prior to the start of this trial, a randomization list will be generated and sealed opaque envelopes will be created for each participant in the study. Each envelope will instruct which ethmoid cavity (RIGHT or LEFT) will receive PuraSinus. During the surgery, after a total ethmoidectomy has been performed bilaterally by the surgeon, the research coordinator or research staff will open the assigned envelope and have the surgeon read which side the PuraSinus should be applied to. The contralateral ethmoid cavity will receive PosiSep X. The research staff or research coordinator will verify that the intervention (PuraSinus) was applied to the assigned ethmoid cavity.

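### Section 13.2 does not name the mixed model's treatment contrast; read off under default 0/1 coding, it would compare different patients on one side and lose the pairing

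*Combined protocol and SAP*

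**What the plan says.** Each patient receives PuraSinus in one ethmoid cavity and PosiSep X in the other. Under section 6.1, "Each envelope will instruct which ethmoid cavity (RIGHT or LEFT) will receive PuraSinus".

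For pain, section 13.2 makes the paired Wilcoxon signed rank test the comparison of the two interventions. It then adds a generalized linear mixed model to take account of side, with a random intercept per participant, and states that "independent variables will include randomized intervention, side, and an interaction of intervention-by-side". The stated purpose of the interaction is to test whether the effect differs between sides. For debridement time and the Lund-Kennedy score, the outcomes "will be compared between interventions using Wilcoxon signed rank and generalize mixed effects model as described above".

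Section 13.2 does not give the coding of the factors, the contrast that counts as the model's intervention effect, or what becomes of the interaction if it is null. For time and Lund-Kennedy it does not say which of the two methods decides.

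Section 13.1 bases the sample size on the Wilcoxon test alone: "a sample of 30 subjects will provide 83% power to detect this difference in paired measures using a Wilcoxon signed rank test".

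**The concern.** The design gets its precision from comparing two sides of the same patient. A model with intervention, side and their interaction has four free means for only two kinds of patient (PuraSinus left, PuraSinus right). In such a model the line labelled intervention in the output depends on how the factors are coded. Under the reference coding that many analysts would use by default, that line is the effect on the reference side. On any one side each patient has only one product, so the comparison is between different patients.

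Two analysts could therefore follow 13.2 to the letter and report treatment effects with quite different standard errors, and the choice could be made after the data are seen. For time and Lund-Kennedy, a clear paired test could stand beside a null model coefficient, with no rule for which to believe.

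**Working it through.** **Inputs.** From section 13.1: difference 2, SD 3.5, two-sided alpha 0.05, 30 patients, stated power 83%, and an SD of 2.80 from the cited study of a comparable packing. Assumed, because the plan does not state them: 3.5 is the SD of the within-patient difference, the sides split 15:15, and the data are normal.

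**The plan's own figure.** A paired noncentral t calculation, with n multiplied by the Wilcoxon efficiency 3/π, gives 83.9%. Simulating the Wilcoxon test gives 83.9% (exact p) and 84.2% (approximate p). The stated 83% is reproduced. It requires 3.5 to be the SD of the difference, or equally a per-side SD of 3.5 with ρ = 0.5. As a per-side SD, 3.5 would give 57% at ρ = 0 and 68% at ρ = 0.22 (paired t).

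**What the coefficient estimates.** Let group A be the patients with PuraSinus on the left and group B those with PuraSinus on the right. Take PosiSep X and left as reference levels, with m the intercept and b1, b2, b3 the coefficients for intervention, side and interaction:

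- A, left (PuraSinus): m + b1
- A, right (PosiSep X): m + b2
- B, left (PosiSep X): m
- B, right (PuraSinus): m + b1 + b2 + b3

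Hence:

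- b1 = A-left − B-left, which compares different patients on one side.
- b3 = (B-left + B-right) − (A-left + A-right), a difference in patient totals and so wholly between patients.
- b1 + b3/2 = ½[(A-left − A-right) + (B-right − B-left)], the equal-weight average of the two within-patient differences.

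If b3 is left out, the two groups have the same expected total. Totals then carry no information on b1, and the estimate of b1 is the same equal-weight average.

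**Variances** (s = per-side SD, 15:15):

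- Var(b1) = 2s²/15, whatever ρ is, so the random intercept does not help.
- Var(b1 + b3/2) = 2s²(1−ρ)/30.
- Ratio = 2/(1−ρ).

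**Numbers.** Holding the SD of differences at 3.5 means 2s²(1−ρ) = 12.25. With s = 2.8, 1−ρ = 12.25/15.68 = 0.78, so ρ = 0.22. The within-patient SE is 3.5/√30 = 0.64 in every row.

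| Per-side SD | ρ | SE of b1 | Variance ratio | Power of b1 (t / normal) |
|---|---|---|---|---|
| 2.475 | 0 | 0.90 | 2 | 57% / 60% |
| 2.8 | 0.22 | 1.02 | 2.56 | 47% / 50% |
| 3.5 | 0.5 | 1.28 | 4 | 33% / 35% |

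The side-averaged contrast has power 86% (t) or 88% (normal) in all three rows. In 600 simulated REML fits at s = 2.8 and ρ = 0.22, b1 had power 50% and the side-averaged contrast 87%. Dropping the interaction also gave 87%, so it gains nothing over averaging. In simulated trials with a true difference of 2, the Wilcoxon test was significant while b1 was not in 26%, 37% and 50% of trials for the three rows in order.

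**Precision of the interaction.** Var(b3) = 4s²(1+ρ)/15. At s = 2.8 and ρ = 0.22 the SE is about 1.6 points, 2.5 times the within-patient SE.

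**The case against.** The strongest reply is that the plan never says it will report a one-side coefficient. With sum-to-zero coding, or an effect averaged over sides, the same model with the same interaction keeps the pairing and loses no power. That is correct. A reader might infer that including the interaction in itself destroys the pairing and leaves about 50% power. The documents do not support this: the loss needs 0/1 coding, which 13.2 does not specify, and 50% is one point in a range that rests on an assumed per-side SD.

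A second reply is that for pain the model is there to look at side, while the Wilcoxon test is the comparison and the only one powered. That also stands. Section 10.1 has the left cavity debrided before the right in every patient, so adjusting for side is sensible. The reply does not cover debridement time and Lund-Kennedy, for which the model is named as a treatment comparison in its own right.

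A reader might also infer a false-positive rate of about 9% per outcome from having two tests. Simulation does give 8.8–9.8%, but only if a win on either test counts and the one-side coefficient is used. The plan states neither. With the side-averaged contrast, an either-test rule gives about 6%.

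Finally, pain is a bounded 1–10 score and the model is called generalized, so normal-theory figures are approximate. The result about coding does not depend on normality.

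**Conclusion.** The point holds as an ambiguity with a material consequence. Section 13.2 specifies a model but not its treatment contrast, and a default reading gives an unpaired, one-side estimate. Its variance is at least twice that of the within-patient effect for any non-negative correlation. Power falls to roughly 33–60% for per-side SDs from 3.5 down to about 2.5, against about 84% for the paired Wilcoxon test and 86–88% for the side-averaged contrast. These powers assume a true difference of 2, an SD of differences of 3.5, a 15:15 split and normal data. They are worked on the pain scale, since the plan gives no SDs for time or Lund-Kennedy; the variance ratio carries over to those outcomes.

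The primary test for pain and its stated 83% power are not affected. The practical weight falls on debridement time and Lund-Kennedy, where two methods are named without a rule for which decides.

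**What to change.** In section 13.2:

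1. For pain, debridement time and Lund-Kennedy, take the model's treatment estimate and 95% CI from intervention plus side plus a random participant intercept. Equivalently, keep the interaction and prespecify the equal-weight average of the left and right effects.
2. Report the intervention-by-side interaction descriptively, noting that it is a between-patient contrast with low precision.
3. State that the Wilcoxon signed rank test is the deciding test for each of these outcomes and that the model supplies the estimate and interval.

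The cost is a few sentences of wording. No new data, patients or procedures are needed.
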